- Current use of oral lopinavir/ritonavir solution (and the inability to switch to a solid dosage form during the entire duration of the study).
- Current use of warfarin.
- ALT or AST > 2 x the upper limit of normal or total bilirubin outside the normal range.

	
 • Creatinine clearance (CrCl) < 50 mL/min by Cockcroft-Gault. • Allergy to rubber or thiuram derivatives
TEST PRODUCT, DOSE, AND ROUTE OF ADMINISTRATION	
Oral disulfiram given as 1000 mg daily (cohort 1) or 2000 mg daily (cohort 2) versus placebo for 5 consecutive days in adults with early symptomatic SARS-CoV-2 infection will be administered in a double-blind fashion.
 
Placebo tablets will be administered in a double-blind fashion and given as a single oral administration on days 1-5.

DURATION OF PARTICIPATION AND DURATION OF STUDY	
Study products will be administered at days 1-5. Participants will be observed on study at days 5, 15, and 31.
 
Participants will be randomized to either of two treatment arms, oral disulfiram or placebo.
 
Screening: up to 7 days prior to treatment randomization.
 
Treatment (for each arm): 5 days (participants to be observed for a total of 4 hours on the last treatment day, Day 5)
 
Follow-up (for each arm): 31 days after the initial dose for that treatment arm.
 
The total duration of the study is expected to be 31 days (approximately 1 month).

CONCOMITANT MEDICATIONS	
The following medications are not allowed during the study because of potential interactions with disulfiram: warfarin; any over the counter drug, food or other product that contains or might contain alcohol; if HIV-positive, specific protease inhibitor preparations (oral amprenavir solution, ritonavir solution, lopinavir/ritonavir solution, soft gelatin form of ritonavir or lopinavir/ritonavir, tipranavir).

EFFICACY EVALUATIONS	
 • Change in plasma inflammatory biomarker levels² • Change in SARS-CoV-2 viral load⁴ • Change in COVID-19 symptom severity³ (5-point scale)
PRIMARY ENDPOINTS	
 • Change in plasma inflammatory biomarker levels² (e.g., IL-6, IL-1β) at days 5, 15, and 31.

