SECONDARY ENDPOINTS	
 • Safety and tolerability • Change in SARS-CoV-2 PCR quantitative viral load⁴ at days 5, 15, and 31. • Change in COVID-19 clinical stage (five-point symptom severity scale³) at days 5, 15, and 31. • Time to recovery (date of symptom onset to date of complete resolution of symptoms) • If applicable, the proportion of participants hospitalized at day 5, 15, and 31. • If applicable, the proportion of participant deaths at day 5, 15, and 31
OTHER EVALUATIONS	
 • SARS-CoV-2 specific T- and B- cell responses⁵ • Pyroptosis (aberrant proinflammatory cell death) assay⁶ • High sensitivity SARS-CoV-2 antibody titer (IgM, IgE, IgA, IgG1, IgG2, IgG3, IgG4) • Changes in host gene and protein expression from matched blood and respiratory (NP) samples at the single cell level (B, T, natural killer, and myeloid cells). • Changes in T- and B-cell receptor (TCR/BCR) repertoire from matched blood and respiratory (nasal/oropharyngeal) samples.
SAFETY EVALUATIONS	All participants will be followed for possible adverse events (AEs) throughout their involvement in the study.
PLANNED INTERIM ANALYSES	A Safety Monitoring Committee (SMC) will be convened and will meet biannually to review all adverse events and the conduct of the study. Serious adverse events will be monitored by the committee on an ongoing basis throughout the study. All main analyses will be conducted on an intention-to-treat basis. Models will assess the relationship between the timing of disulfiram treatment initiation relative to symptom onset and study outcomes for key efficacy/activity endpoints. Stratified analyses will be performed based on symptom severity, as well as laboratory values (e.g., hs-CRP, ferritin, D-dimer levels at baseline).

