5.3 Study Population

5.3.1 Inclusion Criteria

1. Willing and able to provide written informed consent, and
2. Age \geq 18 years, and
3. Recent symptomatic COVID-19 disease (<14 days from symptom onset)

4. Recent SARS-CoV-2 positive test by molecular diagnostic assay within the preceding 7 days, and
5. Not currently hospitalized, and
6. Willing to abstain from any alcohol during the two-week period in which disulfiram will be administered and during the two-week period immediately after disulfiram administration.
7. Both male and female participants are eligible. Females of childbearing potential must have a negative pregnancy test at screening and agree to use a double-barrier method of contraception throughout the study period.

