5.3.6 Study drug administration

Drug will be administered within 72 hours of randomization.

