5.5.11 Follow-Up (Day 31)

5. Questionnaire Evaluation
6. Targeted physical exam and vital signs
7. Clinical lab collection
 - a. Complete blood count with differential, urea, electrolytes, creatinine, calcium, magnesium, phosphate, liver function tests, erythrocyte sedimentation rate (ESR), high sensitivity C-reactive protein (hs-CRP), D-dimer, lactate dehydrogenase (LDH), and ferritin.
8. Samples collected for research (storage)
 - a. Blood: PBMC (CyTOF, single cell sequencing), plasma (plasma SARS-CoV-2 viral load), serum (SARS-CoV-2 serology)
 - b. Nasopharyngeal swab for SARS-CoV-2 viral load
 - c. Saliva for host DNA sequencing and potential future SARS-CoV-2 quantification (RNA levels and anti-SARS-CoV-2 IgA)
 - d. HIV+ participants: a CD4+/CD8+ T cell count and standard plasma HIV RNA assay.
9. Samples collected for research (storage)
 - a. Blood: PBMC (CyTOF, single cell sequencing), plasma (plasma SARS-CoV-2 viral load), serum (SARS-CoV-2 serology)
 - b. Nasopharyngeal swab for SARS-CoV-2 viral load

- c. Saliva for host DNA sequencing and potential future SARS-CoV-2 quantification (RNA levels and anti-SARS-CoV-2 IgA)

5.6 Table 3. COVID-19 symptom severity questions adapted from the Somatic Symptom Scale (SSS-8). 3

Symptom	New occurrence or worsening of pre-existing symptom during illness	When did it start? (MMM/DD/YY) If day cannot be estimated within 3 days of true onset, include month and year and mark day not known.	Skip if start date known. Was it present in the first 3 days of illness?	Are you still experiencing it, meaning in the past 2 days? For recovered phase, add: By this we mean that your initial symptoms you had when you first developed COVID-19 have not gone away.	Skip if still experiencing the symptom. How many days did it last? This is defined as start date to last date experienced.	When the symptom was at its worst, how much did it bother you? Please answer on a scale from 1 to 5, where 1 is NONE and 5 is VERY MUCH.
Feeling feverish	 Yes  No	____/____/____  Day not known	 Yes  DK  No	 Yes  No	 Don't know	 1  3  5  2  4

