From the time to treatment initiation to clinical recovery or improvement, all participants will be censored at the end of follow-up, not at the time of event (e.g., for mortality). Sensitivity analyses will be performed using imputation of missing data to differentiate discontinuation of participants from treatment versus study evaluations.

Duration of fever, duration of symptoms and duration of time to self-reported return to usual health will be summarized with descriptive statistics. Participant-specific durations of fever and symptoms will be compared between study arms using a two-sided stratified Wilcoxon test with a 5% Type I error rate. Total symptom score will be calculated on each day and the participant-specific area under the curve (AUC) over time will also be compared using a two-sided stratified Wilcoxon test. Participants who do not have complete diary cards due to hospitalization or death will be ranked in these analyses as having poorer outcomes than participants who survived without hospitalization.

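### Fever and symptom durations are tested in all randomized participants although none needs fever or symptoms at the first dose, and the time origin is not stated, so values fixed before dosing can dilute the comparison

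*Combined protocol and SAP*

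**What the plan says.** The inclusion criteria (5.3.1) ask for "Recent symptomatic COVID-19 disease (<14 days from symptom onset" and "Recent SARS-CoV-2 positive test by molecular diagnostic assay within the preceding 7 days, and". Neither these nor the exclusion criteria (5.3.2) require a symptom, or fever, to be present at Day 1.

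Further delay is allowed. The synopsis has "Screening: up to 7 days prior to treatment randomization", although 5.5.1 gives Day -3 to Day 1. Section 5.3.6 adds "Drug will be administered within 72 hours of randomization".

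The only written definition of a symptom's duration is the item in Table 3 (5.6): "How many days did it last? This is defined as start date to last date experienced". The synopsis defines a secondary endpoint in the same way: "Time to recovery (date of symptom onset to date of complete resolution of symptoms".

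Section 6.2 then states that "Participant-specific durations of fever and symptoms will be compared between study arms using a two-sided stratified Wilcoxon test" at a 5% error rate, with the main analyses by intention to treat. It names no time origin for these durations and no strata. An earlier sentence in the same section speaks of recovery or improvement measured from the start of treatment. There is a ranking rule for diaries left incomplete by hospitalization or death, but none for a participant whose fever or symptoms had already ended before dosing.

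**The concern.** A fever that ended before the first dose has a duration that treatment cannot alter, yet it is ranked as an outcome. Such values enter both arms and pull the two distributions together. If many participants are in that position, the test could miss a real shortening of illness, and the null result could be read as absence of benefit. Fever is the most exposed outcome because it is usually shorter than the overall symptom course, while the entry window reaches two weeks after onset.

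**Working it through.** **1. The plan's own power figure.** The only stated power (6.1) concerns IL-6: about 80% for a 35% difference. With mean 36.7 pg/mL, SD 12 (printed as ng/mL, read as pg/mL) and 20 v 10 in a cohort:

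- difference = 0.35 × 36.7 = 12.85
- standard error = 12 × √(1/20 + 1/10) = 4.65
- power = Φ(12.85/4.65 − 1.96) = Φ(0.80) ≈ 79%

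The figure reproduces, but it says nothing about durations, and this point does not affect it. No power is stated for fever or symptom duration.

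**2. Dilution in general.** If a fraction f of values is fixed before dosing, the mean shift falls to (1 − f) of its size, and power becomes Φ((z + 1.96)(1 − f) − 1.96), where z is the normal quantile of the undiluted power. From 80% (z = 0.84), f = 10%, 20%, 30%, 40% gives 71%, 61%, 50%, 39%. Power halves only when f reaches about 39% (34% from a base of 50%, 43% from 90%). The documents do not give f.

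**3. Simulation under stated assumptions.** From the documents: 60 participants at 2:1, so 40 v 20 pooled; two-sided 5% Wilcoxon test. Assumed: log-normal total duration with log SD 0.6; onset-to-first-dose delay uniform over 1-14 or 1-7 days; drug halves only the time remaining after the first dose. Here the test is unstratified, because 6.2 names no strata.

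| Outcome | Delay (days) | Resolved before dose | Power, onset origin, all | Power, first-dose origin, all (resolved = 0) | Power, first-dose origin, still affected only |
|---|---|---|---|---|---|
| Fever, median 4 days | 1-14 | 72% | 8% | 6% | 20% |
| Fever, median 4 days | 1-7 | 46% | 14% | not tabulated | 39% |
| Symptoms, median 12 days | 1-14 | 24% | 35% | 30% | 58% |
| Symptoms, median 12 days | 1-7 | 6% | 71% | not tabulated | 76% |

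Rejection with no drug effect was 4-5%.

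**4. Same check with a cohort-stratified test and other medians.**

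| Median (days) | Delay (days) | Resolved | Onset, all | First dose, all | Still affected only |
|---|---|---|---|---|---|
| 5 | 1-14 | 63% | 8-10% | 8% | 26% |
| 5 | 1-7 | 35% | 20% | 18% | 49% |
| 10 | 1-14 | 32% | 24-26% | 21-22% | 49-51% |
| 10 | 1-7 | 9% | 60% | 58% | 69% |
| 20 | 1-14 | 8% | 63-64% | 60% | 73% |

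Under the null at median 10 days, the three analyses rejected in 5.7%, 5.4% and 5.4% of trials. Changing the drug's multiplier at median 10 days and delay 1-14 moves the levels but not the pattern: 36% v 71% at 0.4, and 16% v 31% at 0.6 (onset, all v still affected only).

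**5. Reading the results.** Moving time zero to the first dose does not recover the loss, because resolved participants then enter as tied zeros. The gain comes from restricting on a pre-dose value. It fails only when almost nobody remains: at median 3 days and delay 4-14 days, 93% have resolved, about 60 × 0.07 ≈ 4 participants are left, and no version has useful power (5% v 1%).

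**The case against.** The strongest objection is that the onset origin is not established. Table 3 is a questionnaire item rather than an analysis definition, and the recovery endpoint is a different outcome. Section 6.2 also ties these analyses to diary cards, which are kept during the study, and refers elsewhere to the start of treatment. That stands: a reader might infer that durations are definitely compared from their start dates, but the documents leave the origin open and conflicting. It does not remove the concern, since the first-dose origin loses as much power.

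Second, 14 days is a ceiling. The trial aims at early disease and requires a positive test within 7 days, so typical delays may be short. This also stands. With entry over 1-7 days and median 12-day symptoms, the loss is only 71% against 76%. For fever it persists (14% against 39%).

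Third, the planned test is stratified. Strata based on baseline symptom status would recover a little (about 35% to 41% for symptoms at median 12 days and delay 1-14, with fever unchanged), and stratifying by cohort leaves the pattern intact.

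Fourth, these comparisons are exploratory, are not in the 6.2.2 list, and had no planned power. This is correct and limits the weight of the point. Time to recovery, however, is a secondary endpoint in the synopsis, and the duration comparisons are formal 5% tests.

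Finally, restriction leaves fever with low power. This is also true, and the fix should say so.

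**Conclusion.** The point holds in limited form. Nothing requires fever or symptoms at Day 1, nothing in 6.2 sets such participants apart, and the time origin is unstated with conflicting pointers. Under either origin, values fixed before dosing attenuate the effect.

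The size is conditional on the assumed durations, delays and halving of remaining time. For median 4-day fever, about 46-72% have resolved before dosing, and power is 8-14% against 20-39% when restricted. For median 12-day symptoms, about 6-24% have resolved, and power is 35-71% against 58-76%.

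A reader might infer that many participants are affected and that power is roughly halved. The documents support neither as a general statement: they give no duration, delay or effect, and across the stratified scenarios in the working the share of power kept runs from about a third for short fever (8% of 26%) to nearly 90% for long symptoms (64% of 73%). Nor is this a source of false positives, since type I error stays near 5%. The primary endpoint and its stated power are unaffected.

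**What to change.** In 6.2:

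- Define time zero for fever and symptom durations as the first dose, and reconcile this with Table 3 and the synopsis definition of time to recovery.
- Compare days from first dose to the last day with fever (or symptoms) among participants with fever (or any symptom) on the last record before the first dose. Because that value precedes treatment, the restriction keeps the randomized comparison.
- Report by arm the number already resolved, and describe total duration from onset without a test.
- Apply the same limit to time to recovery.
- Name the strata, and keep the existing ranking rule for hospitalization and death.

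The cost is mostly SAP wording, since start and last dates are already collected. One point of conduct is needed: the Schedule of Evaluations lists a Day 1 symptom check but does not mark it as pre-dose, and Table 3 counts a symptom as current if felt in the past 2 days. The check must therefore be recorded before the dose, and the rule must say what counts as present.

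The tested set falls below 60: about 17-32 for short fever (60 × 0.28 to 60 × 0.54) and about 45-57 for symptoms under these assumptions. Fever power stays low, so that result should be presented mainly as an estimate with its interval.

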6.2.1 Primary endpoint

- Changes in plasma inflammatory biomarker levels² (e.g., IL-6, IL-1 β) at days 5, 15, and 31.

6.2.2 Secondary endpoint(s):

- Safety and tolerability (frequency of Grade 2 or higher adverse events) at days 2, 3, 4, 5, 7, 9, 11, 15, and 31.
- Change in SARS-CoV-2 PCR quantitative viral load⁴ at days 5, 15, and 31.
- Change in COVID-19 clinical stage (five-point symptom severity scale³) at days 5, 15, and 31.
- The proportion of detectable versus not detectable levels of SARS-CoV-2 RNA from site-collected NP swabs at entry, day 5, and day 15 among a subset of participants.

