4.1.8 Disulfiram dose justification

Disulfiram's safety profile has been evaluated in several clinical trials.

In an open-label clinical trial to determine short-term disulfiram on decay of the HIV reservoir in patients on highly active antiretroviral therapy (NCT01286259), patients received 500 mg disulfiram daily via oral administration for 14 days. The safety and tolerability of a two-week course of disulfiram was defined using the Division of AIDS Table for Grading the Severity of Adult and Pediatric Adverse Events, Version 1.0, December 2004 (Clarification, August 2009). A total of 16 patients were recruited, with no adverse event reported during the treatment course.

In a phase 2 non-randomized trial focusing on short-term disulfiram to reverse latent HIV infection (NCT01944371),¹⁰³ patients received disulfiram daily for 5 days at doses of 500 mg, 1000 mg or 2000 mg. The safety and tolerability of disulfiram was defined using the Division of AIDS Table for Grading the Severity of Adult and Pediatric Adverse Events version 2.0, November 2014. Thirty patients were recruited, and all participants completed the study. There were no deaths, drug discontinuations, or grade 2-4 adverse events observed. No adverse events related to the study drug were reported in the 500 mg group, which was consistent with the findings described in the previous trial above. Grade 1 clinical adverse events related to study drug were more common in the higher dosing cohorts including 10 events in the 1000 mg group, and 14 events in the 2000 mg group.

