5.3.4 Treatment

A total of 60 participants will be randomized (2:1) to receive active drug versus placebo in a dose escalation study. The first 30 participants will be enrolled in the 1000 mg dosing cohort, randomized 2:1 to receive either disulfiram 1000 mg (N=20) or placebo (N=10) daily for 5 consecutive days. As long as safety monitoring criteria are met to proceed to the second dose, the next 30 participants will be enrolled in the 2000 mg dosing cohort, randomized 2:1 to receive either disulfiram 2000 mg (N=20) or placebo (N=10) daily for 5 consecutive days.

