6 STATISTICAL PLAN

6.1 Sample Size and Power Considerations

Based on a design with 20 patients per disulfiram treatment group within each dosing cohort (1000 mg, 2000 mg) and a null hypothesis that there will be a differential change in plasma inflammatory cytokine levels (e.g., IL-6) in both groups (disulfiram treatment and placebo compared to baseline), we use reported ranges of plasma IL-6 levels in COVID-19 disease¹¹⁹ to estimate sample size and power. Based on a mean plasma IL-6 level of 36.7 pg/mL (95% CI 21.6-62.3 pg/mL), we estimate that the study will have approximately 80% power to detect a 35% difference in plasma IL-6 levels between the disulfiram versus placebo groups. These measurements will be assessed at day 5, 15 and 31 at the 0.05 significance level using a log-likelihood ratio test and non-linear mixed effect regression modeling. This estimate is based on the assumptions that plasma IL-6 levels are log normally distributed and that the standard deviation of the pre- and post-dose levels is 12 ng/mL (derived from ref: DE Leisman et al. Cytokine elevation in severe and critical COVID-19: a rapid systematic review, meta-analysis, and comparison with other inflammatory syndromes). The adjustments will be made for pre-treatment plasma inflammatory cytokine (e.g., IL-6) levels. Safety endpoints will include the total number of Grade 2 or higher events; the number of Grade 2 or higher events possibly, probably or definitely related to study drug; the number of serious adverse events; and the number and cause for treatment or study discontinuation.

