6.2.4 Analysis of AE data

Analysis of AE data will primarily be descriptive based on MedDRA coding of events. Rates of AE will be compared between randomized arms using Fisher's Exact Test.

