7.3 Safety Reporting Requirements

7.3.1 Reporting Interval

All AEs and SAEs will be documented from the first administration of study product. All AEs and SAEs will be followed until resolution even if AEs extend beyond the study-reporting period. Resolution of an adverse event is defined as the return to pre-treatment status or stabilization of the condition with the expectation that it will remain chronic. At any time after completion of the study, if the investigator becomes aware of a SAE that is suspected to be related to study product.

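### Graded safety endpoints start at Grade 2, while the related events reported at these doses of disulfiram alone were Grade 1; no named endpoint uses mild events, and the Fisher comparison is left undefined

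*Combined protocol and SAP*

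**What the plan says.** - **Endpoint.** Section 6.2.2 lists "Safety and tolerability (frequency of Grade 2 or higher adverse events" by visit. The secondary objectives in the synopsis use the same threshold. Section 6.1 states "Safety endpoints will include the total number of Grade 2 or higher events", then adds related Grade 2+ events, serious events and discontinuations. Where section 5.1.2 and the synopsis endpoint list mention safety and tolerability, they give no grade. No named endpoint is built on Grade 1 events.
- **Test.** Section 6.2.4 says "Analysis of AE data will primarily be descriptive based on MedDRA coding of events" and then "Rates of AE will be compared between randomized arms using Fisher's Exact Test". It names no grade, relatedness, cohort or pooling rule, significance level or sidedness.
- **Capture.** Section 7.3.1 says "All AEs and SAEs will be documented from the first administration of study product". The adverse event log (Table 4) has a box for mild events and five levels of relatedness.
- **Earlier experience.** For the earlier trial of disulfiram alone (30 participants at 500, 1000 or 2000 mg), section 4.1.8 reports: "There were no deaths, drug discontinuations, or grade 2-4 adverse events observed". There were no related events at 500 mg. Related Grade 1 events were commoner at the higher doses, "including 10 events in the 1000 mg group, and 14 events in the 2000 mg group".
- **Size.** Section 5.3.4: cohort 1 is "randomized 2:1 to receive either disulfiram 1000 mg (N=20) or placebo (N=10) daily for 5 consecutive days". Cohort 2 has the same sizes at 2000 mg.

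**The concern.** The graded endpoints sit above the only grade of related event, and the only dose gradient, reported for disulfiram alone in that trial. Tolerability is a named objective and the trial escalates the dose, so mild, short-lived effects are part of the question. The data will be collected, but no endpoint summarises them.

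There is also a weakness in the test. At 20 v 10, Fisher's test is conservative and needs a large imbalance in events before it can reject. If it is applied to Grade 2+ events within a cohort, a non-significant result would say little about either dose.

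**Working it through.** The documents state no power or detectable difference for safety, so there is no figure to reproduce. The check asks what a Fisher comparison within one cohort could detect.

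**Inputs.** 20 active and 10 placebo per cohort (5.3.4). No Grade 2-4 events among 30 participants, and 10 + 14 = 24 related Grade 1 events at 1000 and 2000 mg (4.1.8).

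**Assumptions not in the documents.** About 10 participants per dose group in the earlier trial; two-sided 5% level; placebo rates as shown.

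**Step 1: Grade 2+ rates compatible with a zero count.** The exact two-sided 95% upper limit for 0/n is 1 − 0.025^(1/n); the one-sided limit is 1 − 0.05^(1/n).
- 0/30 (all doses): 11.6% two-sided, 9.5% one-sided
- 0/20 (1000 and 2000 mg together): 16.8%, 13.9%
- 0/10 (one dose): 30.8%, 25.9%

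**Step 2: smallest result that rejects with no placebo events.** Sum the hypergeometric probabilities no larger than that of the observed table.
- 7/20 v 0/10: C(20,7)/C(30,7) = 77520/2035800 = 0.0381. The opposite tail adds 0.0235 + 0.0021 + 0.0001, so p = 0.064.
- 8/20 v 0/10: C(20,8)/C(30,8) = 125970/5852925 = 0.0215. The opposite tail adds 0.0068 + 0.0004, so p = 0.029.

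At least 8 active events are therefore needed.

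**Step 3: exact power.** Power = Σ Bin(a; 20, p1) × Bin(b; 10, p0) over all tables with p ≤ 0.05. Boschloo's two-sided p-value is taken as twice the smaller one-sided value.

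| Grade 2+ rate, active v placebo | Fisher | Boschloo |
|---|---|---|
| 9.5% v 0% | 0.03% | 0.2% |
| 13.9% v 0% | 0.4% | 1.5% |
| 16.8% v 0% | 1.2% | 3.9% |
| 25.9% v 0% | 12% | 24% |
| 30.8% v 0% | 25% | 42% |

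With a placebo background, a 16.8-point excess over 10% gives Fisher 5.8%, and over 20% gives 9.4%. If the cohorts were pooled (40 v 20), 16.8% v 0% gives 36%.

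**Step 4: size.** With equal rates in both arms, Fisher's true error rate at 20 v 10 is 0.45% at a 5% event rate and never exceeds about 3.3%. Boschloo's test rejects every table that Fisher rejects plus six more (one is 7/20 v 0/10), and its size stays below 5%.

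**Step 5: any-grade related events.** Section 4.1.8 counts events, not participants. If 24 events fell at random on 20 participants, the mean is 24/20 = 1.2 and the share affected is 1 − exp(−1.2) = 70%. If events clustered in a few participants, the share is much lower; 30% is shown as an example. Placebo rates are assumed.

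| Any-grade rate, active v placebo | Fisher | Boschloo |
|---|---|---|
| 70% v 10% | 87% | 93% |
| 70% v 20% | 66% | 74% |
| 70% v 30% | 45% | 52% |
| 70% v 50% | 15% | 16% |
| 30% v 20% | 4% | 6% |

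**The case against.** Much of the case on the other side stands.

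- **No safety power was promised.** The adverse event analysis is mainly descriptive, safety is a secondary objective, and section 6.2 calls the study exploratory. Nothing says that a non-significant test would be reported as evidence of tolerability.
- **The test is not tied to Grade 2.** A reader might infer that the Fisher comparison itself starts at Grade 2. Section 6.2.4 sets no grade, and all events are recorded, so on its plain wording mild events could be included. The gap is that the comparison is undefined.
- **Power of about 1% is one scenario.** A reader might take the 1.2% figure as the answer. It combines an upper limit from both doses together with a single cohort and no placebo events in symptomatic COVID-19 patients. One dose throughout gives 25%; both doses pooled throughout gives 36%. Pooling is not specified, however, and would merge the doses under study.
- **Grade 1 events are not the whole known signal.** Section 4.1.4 describes serious effects thought to be dose-related. Section 4.1.8 describes the trial with vorinostat, stopped after two participants had neurological events judged possibly and probably related to disulfiram. A Grade 2 threshold is a defensible response to those signals.
- **Tolerability is also reviewed elsewhere.** Under section 8.1 the safety committee reviews tolerability before the second cohort and may act on patterns of individually minor events. It would be too strong to say that the dose question goes unanswered.
- **The gain is uncertain.** Fatigue, nausea, vomiting and headache are on the COVID-19 symptom list (Table 3), so the placebo background may be high and relatedness hard to judge.

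These points lower the weight of the concern. They do not supply an endpoint for the mild related events or define the comparison.

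**Conclusion.** The point holds as a gap in definition and is worth considering. Every graded safety endpoint starts at Grade 2, the related events reported at 1000 and 2000 mg of disulfiram alone were Grade 1, and no named endpoint summarises mild events that will be recorded anyway.

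Within a cohort of 20 v 10, Fisher's test has roughly 0 to 25% power for Grade 2+ rates compatible with the earlier zero count. That range assumes no placebo events, about 10 participants per earlier dose group and a two-sided 5% level.

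The documents do not support a claim that an any-grade comparison would be well powered. The number of participants affected is not given, and power runs from 4% to 87% with Fisher and from 6% to 93% with Boschloo over the cases shown. The firmer gain is an estimate with an interval for the kind of event already seen. The change of test is the smaller part.

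One caution on the input: section 4.1.5 gives 3 days of dosing for the earlier trial and section 4.1.8 gives 5. These must be reconciled before its counts are relied on.

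**What to change.** 1. In sections 6.1 and 6.2.2, keep the Grade 2+ endpoint and add beside it the proportion of participants with at least one related adverse event of any grade, by randomized arm within each dosing cohort, with an exact confidence interval for the risk difference.
2. Reconcile the relatedness scales: Table 4 has five levels, section 6.1 uses the upper three of them, and section 7.3.4 has only two categories. State also how the mild, moderate and severe boxes in Table 4 map to the DAIDS grades named in section 7.3.3.
3. In section 6.2.4, replace Fisher's test with Boschloo's exact test, which keeps the 5% size and is never less powerful than Fisher at 20 v 10. State the grade, the cohort or pooling rule, alpha and sidedness.

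The cost is SAP wording; no new data or participants are needed. The downside is that Grade 1 events are softer and COVID-19 symptoms add background noise. The blinded placebo arm guards against bias from this but does not remove the loss of precision.
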